IRB # 17-1350

Title: Stimulation Parameters and Non-motor Symptoms in PD Treated With DBS
Version Date: 08/28/2020

Introduction

Deep brain stimulation of the dorsolateral Subthalamic Nucleus is a highly effective treatment for the motor symptoms of moderate to advanced Parkinson's disease. At the same time, however, this therapy is also associated with small but consistent changes in cognitive and affective function. The mechanisms underlying these unintended DBS side effects is unknown. The goal of this research is to systematically evaluate two aspects of stimulation (location and frequency) that may explain the non-motor changes associated with STN DBS.

Background and Significance

A number of outcome studies have looked at neuropsychological and psychiatric function both before and after STN DBS. The overall picture has indicated small declines on verbal fluency tests, executive function, and verbal memory retrieval¹. A number of studies have evaluated cognitive function with stimulation on or off, and there is clear evidence that stimulation does impact cognitive abilities including verbal fluency², facial affect recognition³, timing⁴, and response inhibition⁵. However, the mechanism underlying these changes is unknown.

One hypothesis is that changes in cognitive and affective function are due to spread of electrical stimulation to neighboring non-motor regions of the STN (Jahanshahi, Ardouin et al. 2000; Hershey, Revilla et al. 2004; Czernecki, Pillon et al. 2005; Funkiewiez, Ardouin et al. 2006; Halbig, Tse et al. 2009). The possibility that variability in on-off effects arises from a difference in stimulation location is corroborated by our prior work (____ et al., under review) and others' demonstrating that contact location is relevant to cognitive outcomes from STN DBS^{6,7}

An alternative hypothesis that could explain stimulation effects on cognition concerns the frequency of stimulation. The optimal benefit for motor function occurs with high frequency stimulation, on the order of 130 Hz, although there is some minor variation across patients. Stimulation at this frequency appears to interrupt the pathological beta oscillations that occur in the basal ganglia associated with motor impairments. LFP recording in PD patients suggests that oscillatory activity is important for cognitive function⁸ and high frequency stimulation may interfere with cognitive processing. This fits with Wojtecki and colleagues⁹ finding that verbal fluency performance worsens with high frequency stimulation and improves with low frequency stimulation.

This study will clarify prior observations of cognitive changes in patients with STN DBS²⁷ and opens the door to tailoring stimulation parameters to independently influence cognitive or motor function. For example, DBS technology could be designed to improve both cognitive and motor symptoms by stimulating at one frequency in dorsal STN, and another frequency in ventral STN.

Aim 1. To evaluate the cognitive effects of high frequency stimulation at dorsal and ventral contact locations in PD patients with bilateral subthalamic nucleus DBS electrodes. We hypothesize that, relative to OFF stimulation, performance on tasks involving executive functions will show greater change at ventral contacts than at dorsal contacts.

Aim 2. To evaluate the cognitive effects of low frequency stimulation at dorsal and ventral contact locations in PD patients with bilateral subthalamic nucleus DBS electrodes. We hypothesize that, for tasks where high frequency stimulation produces a *deficit* relative to OFF stimulation (e.g., verbal fluency), low frequency stimulation will *eliminate or reverse* performance changes relative to OFF stimulation.

Aim 3. To characterize changes in cognitive network activity during alternative stimulation of the STN. We will also collect scalp EEG data during task performance when stimulation is OFF compared to alternative DBS settings. Patients with Medtronic or Abbott/St. Jude DBS systems that have been MRI safety tested will also undergo fMRI on a second day to examine BOLD

responses during task performance while stimulation is OFF compared to alternative DBS settings.

Study Design

This is a prospective cohort study. All data will be collected at the Cleveland Clinic over one or more study days. The Figure provides an overview of the study procedures and timing for patients.

Sample

We will recruit 15 patients diagnosed with Idiopathic Parkinson disease.

Inclusion Criteria:

1. Between 40 and 70 years of age,
2. Ability to provide informed consent,
3. Clinical diagnosis of idiopathic Parkinson disease (PD) by a movement disorders neurologist,
4. Disease duration of at least 4 years,
5. Treated with bilateral STN DBS for at least 3 months prior to study enrollment.

Exclusion criteria:

1. History of prior neurosurgical intervention for PD (e.g., DBS, thalamotomy, pallidotomy)
2. History of other central nervous system disease (excluding migraine),
3. Presence of active psychiatric symptoms meeting Diagnostic and Statistical Manual of Mental Disorders-4th Edition (DSM-IV) criteria for Axis-I disorder on formal psychiatric evaluation, with the exception of mild depression (Beck Depression Inventory-2 score below 19),
4. Cognitive impairment meeting Diagnostic and Statistical Manual of Mental Disorders-4th Edition (DSM-IV) criteria for dementia on formal neuropsychological evaluation,
5. Current alcohol or substance abuse,
6. Lack of fluency in English which would invalidate cognitive testing,
7. Hearing or visual impairment precluding cognitive testing.

Exclusion criteria for Imaging procedures:

8. Inability to safely undergo MRI procedure (i.e., metal objects like prostheses, pacemakers)

Controls

We will recruit 20 health controls without Idiopathic Parkinson disease to examine normal performance and EEG variability over repeated task administration.

Inclusion Criteria:

1. Between 3 and 70 years of age,
2. Ability to provide informed consent.

Exclusion Criteria:

1. History of central nervous system disease (excluding migraine),
2. Presence of active psychiatric symptoms meeting the Diagnostic and statistical Manual of Mental Disorders – 4th Edition (DSM-IV) criteria for Axis-I disorder on formal psychiatric evaluation, with the exception of mild depression (Beck Depression Inventory-2 score below 19),
3. Cognitive impairment meeting the Diagnostic and statistical Manual of Mental Disorders – 4th Edition (DSM-IV) criteria for dementia on formal neuropsychological evaluation,
4. Current alcohol or substance abuse,

5. Lack of fluency in English which would invalidate cognitive testing,
6. Hearing or visual impairment precluding cognitive testing

Exclusion criteria for Imaging procedures is not applicable. Healthy controls will only complete EEG monitoring and cognitive testing.

Research Procedures – Arm 1 (12 patients)

Study Day 1: Patients will be admitted to the Clinical Research Unit of the Clinical and Translational Research Center on Study Day 1 after withholding Parkinson's medications overnight. After admission, they will undergo initial stimulation threshold evaluation (for sensorimotor stimulation side effects) with a physician's assistant trained in DBS programming. An EEG technician will apply scalp electrodes and electroencephalogram (EEG) activity will be monitored throughout the Study visit using standard electrophysiological equipment under the supervision of Dr. _____. Subjects will then complete two test sessions, at different stimulation parameters (varying contacts and frequencies designed by Dr. _____ at Case Western Reserve University) at the amplitude corresponding to 90% of side effect threshold.

Test sessions: Each testing session involves performance of several tasks including a phonemic fluency, semantic fluency, Simon task, Facial Affect Recognition task (FAR), Time Production task, Interval Judgment task, as well as a speeded finger tapping test and a group of visual analogue rating scales regarding current mood and well-being (anxiety, motivation, fatigue, physical discomfort).

There will be at least 30 minutes between each session for wash-in/washout of stimulation effects and to rest. Patients will be provided with lunch and additional rest breaks, as needed. At the end

of the last session, patients will take their regular PD medications and stimulation will be readjusted to their clinically-defined settings. Note that STN DBS therapy has a 'wash-in' period of seconds to minutes, while medication therapy typically has a 'wash-in' period of around 15 to 30 minutes. EEG electrodes will be removed and they will be discharged from the CRU when the patient subjectively feels that their stimulation therapy and medications have taken effect, and the supervising neurologist or movement disorder Physician's Assistant delegate observe that Parkinsonian symptoms have improved.

Patient-specific stimulation settings: Deidentified pre- and post-operative imaging will be shared with Dr. _____ at Case Western Reserve University for creation of patient-specific stimulation parameters (Data Use Agreement attached). Patient specific stimulation models for the active cathode/anode that preferentially activate dorsal and ventral aspects of the Subthalamic Nuclei will be constructed prior to the patients' arrival. All stimulation adjustments will be completed by an unblinded Physician Assistant trained in DBS programming. Patients will be blinded to stimulator settings and all data collection will be completed by blinded study personnel. We recognize that it is likely not possible to complete the research sessions for DBS patients in a fully blinded manner: in particular, the off-stimulation state and the low frequency stimulation states may be obvious to both patients and study personnel in the absence of medications. At each session, we will assess patient blinding (i.e., query patients' belief regarding current stimulator setting) to identify those patients who remain blinded for possible subgroup analyses.

Study Day 2: On a second day (scheduled at the subjects' convenience, within 4 weeks of the first study day), patients will again be admitted to the Clinical Research Unit of the Clinical and Translational Research Center after withholding Parkinson's medications overnight. After admission, an EEG technician will apply scalp electrodes and electroencephalogram (EEG) activity from the Epilepsy Monitoring Unit, under the supervision of Dr. _____. Subjects will then complete the three remaining test sessions at different stimulation parameters (varying contacts and frequencies designed by Dr. _____ at the Case Western Reserve University) at the amplitude corresponding to 90% of side effect threshold.

ARM 1

Day 1 Clinical Research Unit

Start Time Minutes Procedure

7:00	15	Informed Consent and Admit to CRU
7:15	60	EEG leads applied
8:15	15	Threshold Evaluation
8:30	30	Setting 1 and wash-in
9:00	30	Test Session 1
9:30	30	Setting 2 and wash-in
10:00	30	Test Session 2
10:30	60	Meds resumed, Clinical settings applied, EEG leads removed, and discharge

Day 2 Clinical Research Unit

Start Time Minutes Procedure

7:00	60	EEG leads applied and admit to CRU
8:00	30	Setting 3 and wash-in
8:30	30	Test Session 3
9:00	30	Setting 4 initiated
9:30	30	Test Session 4
10:00	30	Setting 5 initiated
10:30	30	Test Session 5
11:00	60	Meds resumed, Clinical settings applied, EEG leads removed, lunch, and discharge

Day 3 Research MRI at Mellen Center

Minutes Procedure

20	Safety checklist and MRI prep
20	Setting 1 initiated and position in MRI
30	MRI scan with tasks
20	Extract from scanner, Setting 2 initiated, position in MRI
30	MRI scan with tasks
20	Clinical settings applied, meds resumed

Study Day 3: On a third day (scheduled at the subjects' convenience within 4 to 6 weeks of the first study day), only subjects with MRI-safe DBS systems will undergo fMRI scanning at the Mellen Center Imaging Center after withholding Parkinson's medications overnight. Patients will have their stimulators adjusted (in a randomized order) to OFF and to the patient-specific stimulation parameters that induced maximal cognitive change on Study Day 1. Specific sequences for structural and functional MRI will be determined by Drs. _____ and _____ based on their prior studies demonstrating safety of intracranial electrodes and DBS equipment in MRI environments.¹⁰⁻¹²

Research Procedures – Arm 2 Harmonics (3 patients)

Study Session 1. Patients with MRI-compatible DBS systems will be admitted to the Clinical Research Unit of the Clinical and Translational Research Center for Study Session 1. Patients will be tested while ON their regular Parkinson's medications. We will also record EEG from a sparse electrode array (Fz, Cz, Pz, Oz, F3, F4, C3, C4). At the first session, each patient will have bilateral STN DBS electrodes adjusted by a physician-assistant trained in DBS programming procedures. Settings are adjusted in randomized order to deliver stimulation bilaterally at six low frequencies – 2, 4, 8, 11, 17, and 32 Hz. All other clinical personnel and the patient will remain blinded to stimulation settings. At each setting, patients will remain seated and at rest for a 10-15 minute wash-in period while monitored for sensorimotor or other neurological side effects. They will then perform two of the tasks from the existing protocol (Simon task, Verbal fluency task) for 10-15 minutes. After this 20-30 minute period, stimulation settings will again be changed to another setting. After all 6 settings are completed, patients' stimulation will be returned to their clinically-determined settings and scalp electrodes removed.

Study Session 2. On the same or different day (scheduled at the subjects' convenience maximum of 6 weeks of the first study session), subjects with MRI-safe DBS systems will undergo fMRI scanning at the Mellen Center Imaging Center. Patients will be tested while ON their regular Parkinson's medications. Patients will have their stimulators adjusted (in a randomized order) to each of the six low-frequency stimulation parameters from Study Session 1 and resting-state fMRI scans lasting completed at each setting. Specific sequences for structural and functional MRI will be determined by Drs. _____ and _____

ARM 2

Session 1 Clinical Research Unit

Start Time	Minutes	Procedure
7:00	15	Informed Consent and Admit to CRU
7:15	30	EEG leads applied
7:45	15	Threshold Evaluation
8:00	15	Setting 1 and wash-in
8:15	15	Test Session 1
8:30	15	Setting 2 and wash-in
8:45	15	Test Session 2
9:00	15	Setting 3 and wash-in
9:15	15	Test Session 3
9:30	15	Setting 4 and wash-in
9:45	15	Test Session 4
10:00	15	Setting 5 and wash-in
10:15	15	Test Session 5
10:30	15	Setting 6 and wash-in
10:45	15	Test Session 6
11:00	45	Clinical settings applied, EEG leads removed, lunch, and discharge

Session 2 Research MRI at Mellen Center

Minutes	Procedure
20	Safety checklist and MRI prep
15	Setting 1 initiated and position in MRI
10	MR scan at rest
15	Extract from scanner, Setting 2 initiated, position in MRI
10	MR scan at rest
15	Extract from scanner, Setting 3 initiated, position in MRI
10	MR scan at rest
15	Extract from scanner, Setting 4 initiated, position in MRI
10	MR scan at rest
15	Extract from scanner, Setting 5 initiated, position in MRI
10	MR scan at rest
15	Extract from scanner, Setting 6 initiated, position in MRI
10	MR scan at rest
10	Extract from scanner, Clinical settings applied

____ based on their prior studies demonstrating safety of intracranial electrodes and DBS equipment in MRI environments ¹⁰⁻¹².

Research Procedures – Healthy Controls (20 patients)

Study Day 1: Controls will be not be admitted to the Clinical Research Unit of the Clinical and Translational Research Center; testing will take place in private laboratory space (T2-303). An EEG technician will apply scalp electrodes and electroencephalogram (EEG) activity will be monitored throughout the Study visit using standard electrophysiological equipment under the supervision of Dr. _____. Controls will then complete the remaining study procedures over one 3-hour period.

Test sessions: Controls will complete five 25-minute testing sessions separated by 10-15 minute break periods. Each session will involve performance of several tasks that may include phonemic fluency, semantic fluency, Simon task, Facial Affect Recognition task (FAR), or Interval Judgment task.

Data Analysis

Behavioral Tasks: With the support of a Biostatistics consultant (_____), we propose to evaluate the behavioral task data using a combination of methods for General Linear model and categorical data methods where appropriate. Selected details are presented with the relevant aims above. Statistical corrections will be applied to avoid any increase in family-wise error rate.

EEG: We will analyze event-related potentials (ERP) to trial events in individual tasks to investigate phase-locked activity. Non-phase-locked activity will be investigated by averaging power within alpha, beta, and gamma frequency bands with respect to the trial events. The latter analysis technique will permit identification of event-related desynchronizations (ERD) and synchronizations (ERS)²⁴ associated with non-clinical stimulation parameters.

BOLD: Event-related functional MRI data at all stimulation settings will be analyzed for individual subjects to evaluate patient-specific changes in activated networks. Group-level analyses will be dependent on the degree of similarity across patients in terms of specific cognitive performance changes and associated stimulation parameters.

Confidentiality: CCF study investigators will have sole access to the study data. To protect confidentiality, participants' data will be identified only by coded subject number and stored in a secure location in a de-identified manner. All data provided to Dr. ____ for construction of stimulation models will be de-identified and encrypted. A password-protected, electronic record linking subject numbers with identifying information will be maintained in a password-protected folder on a secure server and only CCF-based study investigators will have access to this file. Data analysis will be conducted by the study investigators in consultation with biostatistics (_____), where appropriate. Dissemination of the results will largely involve aggregate data, although individual data points may be used where illustrative. All dissemination of the study findings will maintain confidentiality and include only de-identified data, except in the situation where express written permission has been obtained from the patient in advance.

Adverse Events and Safety

For Study sessions involving stimulation and EEG recording, the patients are admitted to the CRU with continuous monitoring by nursing staff. Given the minimal risk of the computerized tasks and EEG recordings, the likelihood of adverse events due to the behavioral task or scalp electrodes is very low. Non-clinical or no DBS delivery is expected to worsen some Parkinson's

symptoms temporarily. The Physician Assistant completing the stimulation adjustment and threshold testing will also monitor for patient safety and well-being during parameter changes. In addition, patients will complete ratings scales of their well-being and discomfort at each stimulator setting change, as an additional check on subject safety. For fMRI procedures, Drs. _____ and _____ will closely monitor data integrity and patient safety. They are experts in the safety of MRI scanning in patients with implanted DBS systems.

A Data Monitoring Committee is not planned for this study. The Principal and Co-Investigators, as well as other protections in place (i.e., CRU clinical staff), will continuously monitor subject safety and data integrity. Adverse events and Unanticipated Problems will be reviewed by the Principle and Co-Investigators. If an Adverse Event occurs, it will be recorded on the Adverse Event Summary Sheet, and this will be submitted along with the Adverse Event Report in accordance with the stated time limitations. No clinical electrophysiological report will be generated as the recordings performed do not constitute diagnostic studies. However, if an unexpected finding is observed during the electrophysiological analysis (e.g., seizure activity), consult to the Epilepsy Center will be ordered. Likewise, if an unexpected finding is observed during the MRI procedure (e.g., mass), Dr. _____ will consult with the patient.

Consent

The informed consent process for controls will be completed on the study day prior to EEG electrode application by Dr. _____ or the research coordinator. The informed consent process for patients will be completed by Dr. _____ or the research coordinator/technician in a 2-step process.

Step 1:

For patients approached during a regularly scheduled clinical visit to CCF Main campus: The full procedures, risks, benefits, and alternatives to participation will be reviewed with patients in a private setting (i.e., exam room). Potential participants will be given a copy of the full written consent document (either with or without Study Day 3, depending on the type of DBS system implanted) and are given the opportunity to review the document and ask questions or clarifications of the person conducting the consent interview. The patient is also permitted to discuss the matter with their spouse/caregiver privately before consenting to participate. Patients who wish to proceed will provide limited written consent to access their neuroimaging data obtained as part of routine clinical care for pre-surgical planning and post-operative electrode placement confirmation, de-identify those scans, and deliver them in encrypted format to Dr. _____ for creation of patient-specific stimulation parameters.

For patients not seen in clinic: A letter will be mailed to potential subjects (see Recruitment letter), which includes the screening consent and the main study consent. Study personnel will conduct a follow up phone call (See Screening Telephone Script) to ensure that patients received the letter and to review the main study and the initial screening consent. If the patient agrees to participate, he/she will be asked to sign the screening consent and return it via the self-addressed and stamped envelope provided in the mailing. Upon receipt of the signed screening consent, de-identified scans will be transmitted to Dr. _____ at CWRU. The appropriate confirmation letter (see Confirmation letters – ScreenIn or ScreenFail) will be sent to patient to inform them of whether personalized stimulation models could or could not be constructed. For those patients who screen in, there will be a follow up phone call to serve as the main study consent discussion (See Consent Telephone Script) and to schedule an appointment at the CRU, if the patient provides verbal consent to participate).

Step 2:

Patients will be consented with the full informed consent process when they arrive at the CRU for the first Study Day. The consent process will take place in a private CRU inpatient room.

When patients return for additional study sessions, they will be reminded, before study procedures commence, that they may withdraw consent at any time without consequences.

References

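### Arm 1 fMRI: the rule for choosing the active scan setting names Study Day 1 only, although three of the five settings are tested on Study Day 2

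*Combined protocol and SAP*

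**What the plan says.** The section Research Procedures – Arm 1 spreads cognitive testing over two days. For Study Day 1: "Subjects will then complete two test sessions, at different stimulation parameters". For Study Day 2: "Subjects will then complete the three remaining test sessions at different stimulation parameters". The Arm 1 timetable agrees. Day 1 holds Settings 1 and 2; Day 2 opens with "Setting 3 and wash-in" and runs to Setting 5.

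The Study Day 3 paragraph then defines two scan conditions for patients with MRI-safe systems. One is OFF; the other is the "patient-specific stimulation parameters that induced maximal cognitive change on Study Day 1". This is the only rule for choosing the Arm 1 scan setting, and it does not mention Study Day 2.

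The five settings are not listed. Aim 1 concerns high-frequency stimulation and hypothesises that, "relative to OFF stimulation, performance on tasks involving executive functions will show greater change at ventral contacts than at dorsal contacts". Aim 2 is "To evaluate the cognitive effects of low frequency stimulation at dorsal and ventral contact locations". Aim 3 places the fMRI on a second day, whereas the Arm 1 procedures and the Consent section make it Study Day 3.

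**The concern.** The purpose of the rule is to image each patient at the setting that moved cognition most. A rule that looks at Day 1 alone sees two of the five tested settings, so it can miss the setting it is meant to find.

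The Arm 1 scan has one active condition, compared with OFF. If the setting with the largest change was tested on Day 2, that patient is never scanned at it, and no later analysis can recover the missing scan. The choice also bears on pooling: the BOLD paragraph under Data Analysis makes group-level analysis depend on how alike patients are in their cognitive changes and in the settings that go with them.

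**Working it through.** **Step 1: the plan's own count.** Sessions on Day 1 (Study Day 1 text and timetable): 2. Sessions on Day 2 (Study Day 2 text and timetable): 3. Total 2 + 3 = 5, matching Settings 1 to 5 in the timetable. Text and timetable agree with each other, so the mismatch lies in the selection rule.

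**Step 2: what the rule can see.** Eligible under a literal Day 1 rule: 2 of 5 settings. Not eligible: 5 − 2 = 3 of 5. This step needs no assumption about what the settings are or the order in which they are given.

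**Step 3: what that means for active settings.** Assumption, inferred from Aims 1 and 2: the five settings are OFF plus dorsal and ventral contacts at high and low frequency, that is 1 + 2 × 2 = 5. There are two cases.

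| Where OFF is tested | Active settings on Day 1 | Eligible | Excluded |
|---|---|---|---|
| Day 1 | 2 − 1 = 1 | 1 of 4 | 3 of 4 |
| Day 2 | 2 | 2 of 4 | 2 of 4 |

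In the first case only one active setting is available, so looking for the maximum involves no choice. In the second there is a choice, but between two of the four.

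**Step 4: can a number of patients be given?** That would need the order in which Arm 1 patients receive the five settings. The protocol states randomisation for the Arm 1 scan order ("Patients will have their stimulators adjusted (in a randomized order) to OFF") and for Arm 2 ("Settings are adjusted in randomized order to deliver stimulation bilaterally at six low frequencies"), but gives no order for the Arm 1 test sessions. Suppose every patient had the same fixed order and the same maximal setting. The rule would then miss it in 0 of 12 patients if that setting fell on Day 1, and in 12 of 12 if it fell on Day 2. The documents do not narrow this range. The 12 is itself a ceiling, because only patients with MRI-safe systems are scanned.

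**Step 5: could Day 2 results be used?** Day 2 is due no later than 4 weeks after Day 1. The scan is on a third day, with a window given as within 4 to 6 weeks of Day 1. Day 2 results would normally exist before the scan. The two windows can meet at week 4, where time for scoring would be short.

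**The case against.** The strongest reply is that this is leftover wording and that staff will use both days. There is some support for it. Aim 3 still speaks of a second day for fMRI. The Arm 1 test-session text offers lunch, while the Day 1 timetable ends in discharge and lists lunch only on Day 2. Study Day 1 may once have covered all the behavioural testing. This is plausible but not proved, and it supports correcting the sentence. What stands is that the loss is nil if all five sessions are used in practice.

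A reader might infer that the rule cannot work at all when OFF falls on Day 2, for want of a Day 1 reference. The documents do not support this. Nothing requires OFF to be measured on the same day. With five settings over two days, Aims 1 and 2 must already compare some settings with OFF across days. The two Day 1 settings could be compared with a Day 2 OFF session and one of them chosen.

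A reader might also turn 3 of 5 into 60% of patients, or 0.6 × 12 = 7.2 scanned at the wrong setting. That requires random session order, which is not stated for the Arm 1 tests. It would also count only how often the maximal setting is ineligible; it would not show how much BOLD information is lost. A scan of OFF against a non-maximal active setting still has some value.

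Finally, the scope is narrow. BOLD data are analysed patient by patient first, and the plan already allows for scanned settings that differ between patients. This limits the consequence but leaves the inconsistency in place.

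**Conclusion.** The point holds as an internal inconsistency that should be fixed. The scan-selection rule names one testing day where the procedures have two, and read literally it bars three of the five tested settings from being the active fMRI condition. Confidence in the mismatch is high, since it rests on the text and timetable alone. The figures of one or two eligible active settings out of four rest on the inference that the five settings are OFF plus four active ones.

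The number of patients affected cannot be determined. The consequence is limited to the Arm 1 fMRI part of Aim 3, in at most 12 patients. The behavioural comparisons in Aims 1 and 2 and the EEG analyses do not depend on this rule, so a wider reading that the trial's cognitive results are compromised is not supported.

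**What to change.** Reconcile the Study Day 1, Study Day 2 and Study Day 3 paragraphs of Arm 1. Either state that the active research-scan condition is selected from the cognitive results of all five test sessions on Study Days 1 and 2, or state why Day 2 results are excluded. Align the scan day in Aim 3 with Study Day 3.

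Under the first option all 5 tested settings feed the selection instead of 2. On the OFF-plus-four assumption, that makes 4 of 4 active settings eligible instead of 1 or 2.

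The cost is protocol wording, with no extra visit, scan or patient. The one practical burden is that Day 2 must be scored before the scan, which may be tight when Day 2 falls near week 4. Which score defines the maximal change is a separate question that this edit does not settle.

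### Arm 2 gives six frequencies to three patients in an order described only as randomised; a position-balanced, connected list plus a linear position term would remove most chance confounding with test position at no cost in patients or time.

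*Combined protocol and SAP*

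**What the plan says.** The Arm 2 heading under Research Procedures sets the size: "Arm 2 Harmonics (3 patients". Each patient receives "six low frequencies – 2, 4, 8, 11, 17, and 32 Hz". In Study Session 1, "Settings are adjusted in randomized order to deliver stimulation bilaterally at six low frequencies". At each setting, "patients will remain seated and at rest for a 10-15 minute wash-in period", and then "They will then perform two of the tasks from the existing protocol (Simon task, Verbal fluency task) for 10-15 minutes". The Arm 2 timetable runs six such blocks of 15 + 15 minutes, from 8:00 to 11:00.

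In Study Session 2 the stimulators are "adjusted (in a randomized order) to each of the six low-frequency stimulation parameters from Study Session 1", with a resting-state scan at each setting. That timetable allows 15 minutes for setting and positioning and 10 minutes for the scan.

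Neither session description mentions a Latin square, counterbalancing or any other restriction across patients. The Data Analysis section proposes general linear model and categorical methods for the behavioural tasks and names no position or period term. The Controls section recruits 20 healthy people partly to see how performance and EEG vary when tasks are repeated. They complete five sessions, not six, and no use of their data to correct Arm 2 is specified.

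**The concern.** The same two tasks are repeated six times over three hours, so scores may drift with practice or fatigue. Each frequency is seen only three times, once per patient. Chance imbalance in order is largest when the number of patients is smallest, and here nothing is described that limits it. A frequency that happens to fall early in two or three patients would carry the early-session level of performance with it. When the three patients are pooled or compared, that frequency could look better or worse for no reason other than its place in the sequence. In the MRI session there is no task to practise, but any drift over the scanning period raises the same issue.

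**Working it through.** The documents give no power, effect-size or balance figure for Arm 2, so there is nothing to reproduce. The design itself can be computed.

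**Inputs.** Three patients, six frequencies, each once per patient: 18 observations (Arm 2 text). Blocks of 30 minutes in Session 1 and 25 minutes in Session 2 (Arm 2 timetables). *Assumption:* the three orders are independent random permutations.

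**1. Independent random orders.**
- The variance of one position is (6² − 1)/12 = 35/12. The SD of a frequency's mean position over three patients is √(35/36) = 0.99.
- Simulation gives an average gap between the earliest and latest mean position of 2.75 (5th to 95th percentile 1.33 to 4.00). In time, 2.75 × 30 is about 82 minutes in Session 1 and 2.75 × 25 is about 69 minutes in Session 2.
- The gap is at least 2 positions in 86% of draws and at least 3 in 47%.
- The within-patient sum of squares of position is 3 × 17.5 = 52.5. The share lying between frequencies, R² = 3 Σ(mean position − 3.5)²/52.5, has expected value 5/15 = 0.33 (5th to 95th percentile 0.09 to 0.64).
- At least one frequency falls at the same position in two or more patients in 96% of draws.

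**2. A balanced set.** Take A-B-C-D-E-F, E-C-F-A-D-B and F-D-B-E-C-A.

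| Frequency | Positions | Sum |
|---|---|---|
| A | 1, 4, 6 | 11 |
| B | 2, 6, 3 | 11 |
| C | 3, 2, 5 | 10 |
| D | 4, 5, 2 | 11 |
| E | 5, 1, 4 | 10 |
| F | 6, 3, 1 | 10 |

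- No frequency repeats a position. Mean positions are 3.33 or 3.67, so the gap is 0.33 (10 minutes in Session 1). Exact equality is impossible because 3 × 3.5 = 10.5 is not a whole number.
- R² = 3 × 6 × (1/6)²/52.5 = 0.5/52.5 = 0.0095. The reduction is 1 − 0.0095/0.333 = 97%.
- For a log-shaped practice curve the overlap is 2.6%.
- For position as a six-level factor the overlap is [Σn²/9 − 1]/5, where n counts how often each frequency takes each position. Here that is (18/9 − 1)/5 = 20%, against an expected 33% under random order.
- Of the 15 ordered neighbour pairs, 13 are distinct (E-C and D-B each occur twice).

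**3. What a position term can do.**
- *Linear term.* Mean efficiency for frequency contrasts is 0.89 under random order. Under the balanced set it is 5/(4 + 1/(1 − 0.0095)) = 0.998. Residual degrees of freedom are 18 − 1 − 2 − 5 − 1 = 9.
- *Six-level factor.* Under random order mean efficiency is 0.44, and some contrasts are inestimable in 21% of draws. For the set above, the model with patient, frequency and position has full rank (13). Efficiency is 5/(1.8 + 1.8 + 1.125 + 1 + 1) = 0.74, with 5 residual degrees of freedom.

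**4. Size in outcome units.** The drift per position, *b*, is not in the documents, so a range is assumed, in within-patient SDs. The error SE of a pairwise frequency contrast is √(2/3) = 0.82. Without a position term, random order adds an SD of *b* × √(2 × 35/36 × 6/5) = 1.53*b*; the balanced set caps the bias at *b*/3.

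| Assumed drift *b* | Added SD, random order | Maximum bias, balanced |
|---|---|---|
| 0.1 | 0.15 | 0.03 |
| 0.3 | 0.46 | 0.10 |
| 0.5 | 0.76 | 0.17 |

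**The case against.** The strongest reply is that Arm 2 is exploratory. It has three patients and no aim, hypothesis or group test of its own. The BOLD plan starts with individual subjects and makes group analysis conditional. Within one patient each frequency has exactly one position, so balancing across patients does nothing there. The MRI session is at rest, so the task-practice argument does not carry over to it. At a drift of 0.1 SD per position, the added SD of 0.15 is small beside an error SE of 0.82. All of this stands and limits the weight of the point. It does not remove it, because any pooling or comparison across the three patients is exposed and the remedy is free.

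A reader might also infer more than the documents support:
- *That simple randomisation is planned.* The text says only that the order is randomised. A restricted list would be consistent with it; what is missing is a description.
- *That frequency and position cannot be separated.* A linear position covariate would keep about 89% efficiency on average even under random order. The plan does not exclude such a term; it does not name one.
- *That the results are systematically biased.* The problem is chance imbalance in one small draw.
- *That balancing removes the problem altogether.* It nearly does so for linear or smooth monotone drift, but not for a jump confined to the first or last block, where the overlap stays at 20%.

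**Conclusion.** The point holds as a modest, free improvement. The plan describes neither balancing nor a position term for six settings in three patients. If orders are independent, an average gap of 2.75 positions and a one-third overlap are to be expected, and luck reaches the best balance (R² ≤ 0.01) in fewer than 0.1% of draws. A chosen list brings the gap to 0.33 and the linear overlap to about 1%.

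This rests on two assumptions: that orders would otherwise be drawn independently, and that some drift with position exists. The second is plausible given six repetitions, but the documents do not quantify it. The documents plan no claim about a best or worst frequency, so the consequence is a risk to interpretation rather than to a stated test. Random error remains large with three patients whatever the order.

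**What to change.** State the ordering scheme in both Arm 2 session descriptions. If a balanced scheme is already intended, one sentence settles the matter. Otherwise:

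1. Use a set of three orders that is both position-balanced and connected, for example A-B-C-D-E-F, E-C-F-A-D-B and F-D-B-E-C-A. Assign frequencies to letters and patients to rows at random.
2. Make a fresh draw of letters and rows for the MRI session.
3. Name a linear position term in the Arm 2 behavioural model.

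The set must be chosen with care. With the first order fixed, 156 ordered solutions have no repeated position and sums of 10 or 11, and 12 of them are disconnected. For example, using D-F-B-E-A-C as the third order makes all 15 neighbour pairs distinct, but A, D and E then occupy only positions 1, 4 and 5, and B, C and F only 2, 3 and 6. The contrast between those two groups cannot be estimated with position as a factor (rank 12, not 13). Three arbitrary rows of a 6 × 6 Williams square are not safe either: their linear R² ranges from 0.01 to 0.44.

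The cost is preparing the list and one residual degree of freedom. No patient, visit or time is added, frequencies and durations stay as written, and randomisation and blinding are kept. Carry-over remains only partly addressed, since three patients give 15 transitions for 30 ordered pairs; the protocol should say so.
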